6.4 Subject Disposition

Subject disposition will be listed and summarized as follows:

- The number of subjects who are in each analysis set will be summarized for all enrolled subjects by cohort and overall.
- The number of subjects who failed screening and the reasons for failure will be tabulated overall.
- The number of subjects who complete the study will be tabulated for all enrolled subjects by cohort and overall.
- The number of early terminations and the primary reasons for terminations will be tabulated for all enrolled subjects by cohort and overall. Secondary reasons for termination will be listed.
- Disposition data for all subjects screened will be listed.

6.5 **Protocol Deviations**

A listing of protocol deviations will be provided within Appendix 16.2. Protocol deviations will be categorized as either major or minor by Eisai prior to DB lock.

6.6 Inclusion and Exclusion Criteria

A listing of violators of the inclusion and exclusion criteria will be provided within Appendix 16.2.

6.7 Baseline Assessments

Standard continuous or categorical variable summaries will be presented by cohort and overall for the following variables based on the Safety Analysis Set.

- Demographic data, data for all screened subjects will be listed.
- Weight at screening (kg)
- Height at screening (cm)
- BMI at screening (kg/m²)
- Child Pugh Score
- Recalculated MELD Score (Initial MELD score will be listed only)
- Serum Albumin at Screening
- Total Bilirubin at Screening
- PT at Screening
- INR at Screening
- Creatinine at Screening

6.8 Medical History

Medical and surgical history and current medical conditions will be recorded at the Screening Visit. Separate listings of previous and ongoing conditions at screening will be presented for the Safety Analysis Set. Conditions will be coded using the Medical Dictionary of Regulated Activities (MedDRA) primary system organ class and preferred term.

6.9 Prior and Concomitant Medications

All investigator terms for medications recorded in the CRF will be coded to an 11-digit code using the World Health Organization Drug Dictionary (WHO DD) drug codes. Non pharmacological procedures will be recorded in the CRF but not coded. Prior and concomitant medications will be listed. Prior medications will be defined as medications that stopped before the first dose of lemborexant. Concomitant medications will be defined as medications that started before the first dose of study drug and were continuing at the time of the first dose of study drug, or started after the date of the first dose of study drug.

6.10 Viral Serology

A listing of viral serology results will be provided within Appendix 16.2.

6.11 Urine drug and alcohol screening

A listing of urine drug and alcohol screening results will be provided within Appendix 16.2.

6.12 Pregnancy Test

A listing of serum and urine pregnancy test results will be provided within Appendix 16.2.

6.13 Exposure to Study Drug

A listing of dosing information will be provided within Appendix 16.2.

6.14 Efficacy Analyses

Not Applicable

6.15 Pharmacokinetic Analysis

The Safety Analysis Set will be used for individual plasma concentration listings. The PK Analysis Set will be used for summaries of plasma concentrations and for analyses, summaries, and listings of PK parameters.

Blood samples (4 mL each) for PK assessments of lemborexant and its metabolites (M4, M9, and M10) will be collected at predose (0 hour), 0.5, 1, 1.5, 2, 3, 4, 6, 8, 12, 24, 48, 72, 96, 120, 144, 168, 216, 264, and 312 hours postdose. In addition, blood samples for protein binding (12 mL per time point) of lemborexant and metabolites will be collected at 1 and 24 hours postdose matching the PK sample collection at those time points.

For presentation of the individual data, BLQ values prior to the first non-zero concentration will be set to zero in the linear plots; BLQ values after the first non-zero concentration will be set to missing in the linear plots; and all BLQ values will be set to missing in the semi-logarithmic plots.

For calculation of mean concentrations, all BLQ values will be assigned as zero. If the proportion of values reported as BLQ is more than 50% or if the calculated mean is less than the lower limit of quantification (LLOQ) at a given sampling time, the mean will be treated as follows: zero for time points prior to the first non-zero mean concentrations in the linear plots; missing for time points after the first non-zero mean concentration in the linear plots; and missing for all BLQ values in the semi-logarithmic plots.

Plasma concentration data will be tabulated by nominal time and summarized by analyte and group using descriptive statistics [number of observations (n), arithmetic mean, standard deviation (SD), minimum (min), median and maximum (max)].

Mean plasma concentration-time data (using linear and semi-logarithmic scales) will be presented graphically; mean data will be plotted using nominal sample times.

PK parameters for lemborexant and its metabolites (M4, M9, and M10) will be calculated as described in section 6.2.3.

The adjusted regression coefficient (R^2 adj), number of time points used in the lambda-z estimates, and the lower and upper times of the lambda-z range will also be listed.

PK parameters will be summarized overall by treatment and by treatment stratified by analyte and group using descriptive statistics (n, mean, SD, min, median, max, geometric mean, CV%, calculated as: sqrt(exp[std^2 of log transformed data]-1)*100]).

The rules for presenting raw individual values and summary statistics for PK concentration and parameter data are provided in section 6.3.1.

Protein Binding

Blood samples for plasma protein binding for lemborexant will be collected for each subject at 2 time points: 1 hour and 24 hours postdose. Protein binding data will be provided by the vendor to WCT as a percentage; if more than one value is available for either time point, the average of the protein binding values will be used in the calculations. Protein binding results will be presented as fractions and percentages.

Protein binding will be calculated for metabolites without any assessment of PK parameters.

Evaluation of the impact of hepatic impairment on drug exposure:

The effect of hepatic impairment on the PK of lemborexant, the primary PK parameters based on total C_{max} , $AUC_{(0-72h)}$, $AUC_{(0-t)}$, and $AUC_{(0-inf)}$ will be compared between the cohort of healthy normal controls and the cohorts of subjects with mild and moderate hepatic impairment as defined by Child-Pugh classes A or B. A general linear model of logarithmically transformed values with hepatic function class as a fixed effect will be utilized to estimate the geometric mean ratio (and two-sided 90% confidence intervals) of subjects with mild/normal and moderate/normal hepatic function. Similar statistical analyses will be conducted for the PK parameters of the metabolites and unbound lemborexant as secondary endpoints. Protein binding will be calculated for metabolites without any assessment of PK Parameters. Summary statistics will be generated for each of the PK parameters for each Child-Pugh class and healthy controls

Scatter plots of PK parameters (C_{max}, AUC₍₀₋₇₂₎, AUC_(0-t) and AUC_(0-inf)) of lemborexant and its metabolites versus Child-Pugh Score at Screening will be provided. The association between the primary PK parameters and Child-Pugh Score will be evaluated by regression analysis (the PK parameter as a dependent variable and Child-Pugh Score as an independent variable). For subjects in the Healthy cohort the Child-Pugh score will be set to zero in the scatter plots and regression analysis. Similar analyses will be performed for the following measurements at Screening: MELD score, serum albumin, total bilirubin, PT, and creatinine. Additionally, association between the PK parameters and liver transaminase levels at Screening (ALT and AST) will be performed, if deemed necessary.

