7.2 Study Rationale

This study is being conducted to assess whether mild or moderate hepatic impairment influences the PK and metabolism of lemborexant, with the findings of this study anticipated to guide future dosing recommendations in patients with various degrees of hepatic impairment. Based on data from drug interaction with itraconazole as well as CYP3A-mediated metabolism being the predominant clearance pathway for lemborexant, it is anticipated that a strong effect will be observed in severe hepatic impaired subjects, which will impact the PK of lemborexant, thus leading to contraindications in this subgroup of hepatic impairment subjects. To mitigate the anticipated effect of hepatic function on lemborexant disposition, ongoing Phase 3 studies do not include subjects with severe hepatic disease, however, they do allow for enrollment of subjects with mild and moderate impairment, which likely reflects the anticipated insomnia patient population Therefore, the proposed study limits the population to mild and moderate impaired subjects only. Furthermore, a population PK analysis applied to data from phase 2 and 3 studies will also be utilized to formulate a comprehensive dosing recommendation relevant to the mild and moderate hepatic-impaired subjects.

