9.2 Discussion of Study Design, Including Choice of Control Groups

This single dose, parallel-group study aims to investigate the effects of mild and moderate hepatic impairment on the PK of lemborexant and its main metabolites (M4, M9, and M10). At least 24 subjects will be enrolled, and 16 of these subjects will have impaired (mild or moderate) hepatic function. The other approximately 8 subjects will be healthy and will serve as the control group. Healthy subjects will be matched (1:1) with the 8 subjects with mild hepatic impairment and the 8 subjects with moderate hepatic impairment according to age (± 10 years), sex, and BMI ($\pm 20\%$).

The data from this study will help guide specific dosing recommendations in insomnia disorder and/or ISWRD patients with impaired hepatic function and establish labeling recommendations for this new chemical entity.

Adjudication Committee (revised per Amendment 01)

An independent Adjudication Committee will be employed at intervals to review, in a blinded manner, AEs that could potentially be considered cataplexy or seizure. A set of preferred terms constituting a customized Medical Dictionary for Regulatory Activities (MedDRA) query for cataplexy or seizure will be used to identify events for adjudication (including cataplexy, muscle fatigue, muscular weakness, muscle tone disorder, hypotonia, drop attacks, slurred speech, diplopia, falls, convulsions [standardized MedDRA query (SMQ) narrow and broad], atypical migraine, loss of consciousness, decreased consciousness, myoclonus, syncope, transient global amnesia, lipothymia, [faintness] and transient ischemic attack). To assist in the preparation of narratives about such events and to support the committee's adjudication process, investigators and site staff will be instructed to query subjects who report any of the above events for supplemental information using a questionnaire for events potentially related to cataplexy and the serious adverse event (SAE) form for any of the above events serious.

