9.3 Selection of Study Population

A total of 24 subjects will be enrolled in each of the following 3 cohorts:

Cohort A: 8 subjects with mild hepatic impairment (Child Pugh Class A)

Cohort B: 8 subjects with moderate hepatic impairment (Child Pugh Class B)

Cohort C: At least 8 healthy subjects (control) matched to subjects in Cohorts A and B

Subjects who do not meet all of the inclusion criteria or who meet any of the exclusion criteria will not be eligible to receive study drug.

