9.4.3 Method of Assigning Subjects to Treatment Groups

Subjects will be assigned to 1 of 3 cohorts: subjects with mild hepatic impairment (Child Pugh Class A) will be in Cohort A, subjects with moderate hepatic impairment (Child Pugh Class B) will be in Cohort B, and healthy (control) subjects will be in Cohort C. To qualify for Cohort A or B, the subject must have stable (ie, without any change in disease status for at least 60 days prior to study screening) hepatic impairment conforming to Child-Pugh

classification A or B, respectively (see Table 1 and Table 2), documented by medical history and a physical examination. To qualify for Cohort C, the healthy subject must match a subject with hepatic impairment with regard to age (± 10 years), sex, and BMI ($\pm 20\%$), and as determined by no clinically significant deviation from normal in medical history, physical examination, ECG, and clinical laboratory determinations.

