6 PLANNED ANALYSES

No statistical analysis plan (SAP) prepared in advance of the data can be absolutely definitive and the final clinical study report (CSR) may contain additional tables or statistical tests if warranted by the data obtained. The justification for any such additional analyses will be fully documented in the final CSR.

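### Does matching controls on age, sex and BMI oblige the SAP to prespecify a model adjusted for those factors?

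*SAP*

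**What the plan says.** SAP 6.15 and protocol 9.7.1.7.1 give the same analysis of the primary parameters. In the SAP's words, "A general linear model of logarithmically transformed values with hepatic function class as a fixed effect will be utilized". The stated purpose of that model is "to estimate the geometric mean ratio (and two-sided 90% confidence intervals) of subjects with mild/normal and moderate/normal hepatic function". Neither text names age, sex, BMI or a matched-set term. The other regressions in SAP 6.15 each relate a PK parameter to one liver or laboratory marker. The addendum issued after database lock adds AUC(0-8), unbound-fraction summaries and figures, but no adjusted model.

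Balance between cohorts is dealt with at enrolment. Protocol 9.2 states: "Healthy subjects will be matched (1:1) with the 8 subjects with mild hepatic impairment and the 8 subjects with moderate hepatic impairment", on age (±10 years), sex and BMI (±20%). Being matched is itself inclusion criterion 6 for the healthy cohort (protocol 9.3.1). Protocol 9.3 describes Cohort C as "At least 8 healthy subjects (control) matched to subjects in Cohorts A and B". Protocol 9.4.3 is worded for the individual control: "the healthy subject must match a subject with hepatic impairment with regard to age", and likewise on sex and BMI.

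SAP 6.7 summarises demographic data and BMI by cohort. SAP 6.6 adds: "A listing of violators of the inclusion and exclusion criteria will be provided within Appendix 16.2".

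**The concern.** The groups are defined by disease and not by randomisation, so comparability rests on the matching. The sponsor chose age, sex and BMI as the factors to control, and the analysis then leaves them out. The tolerances apply subject by subject. Every match could comply while one cohort is on average up to 10 years older, or up to 20% different in BMI. One control group also has to serve two impaired cohorts, and protocol 9.4.3 can be read as asking for a match to only one impaired subject.

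If those factors predicted exposure and were unbalanced, a ratio that feeds dosing and labelling recommendations would be biased. If they predicted exposure and were balanced, the class-only interval would be wider than it needs to be. Any adjustment would be chosen after the data were seen, because SAP 6 says only that "the final clinical study report (CSR) may contain additional tables or statistical tests if warranted by the data obtained".

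**Working it through.** **Inputs.** From SAP 4 and protocol 9.7.2: SD of log AUC(0-inf) 0.391, 8 subjects per cohort, two-sided 90% interval, stated half-width 0.322. From protocol 9.1: tolerances of ±10 years, same sex, ±20% BMI. The documents give no effect of age, sex or BMI on lemborexant exposure, so every such effect below is an assumption.

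**1. The plan's own figure.** SE = 0.391 × √(1/8 + 1/8) = 0.1955. Half-width = 1.645 × 0.1955 = 0.3216, which rounds to the stated 0.322; exp(0.322) = 1.38. With the t quantile of the planned three-class model (21 df) it is 1.7207 × 0.1955 = 0.336. Adding age, sex and BMI leaves 18 df: 1.7341 × 0.1955 = 0.339 if the covariates are balanced and explain nothing.

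**2. Size of the gap that matching leaves.** Matched sets were drawn symmetrically within the tolerances (controls aged 40–68, BMI 23–32, assumed). The absolute difference in cohort means was:

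| Factor | Median gap | 95th percentile | Assumed effect | Factor on the ratio: median; 95th percentile |
|---|---|---|---|---|
| Age | 1.4 years | 4.0 years | 0.5–1% per year | exp(1.4 × 0.005 to 0.01) = 1.007–1.014; exp(4.0 × 0.005 to 0.01) = 1.02–1.04 |
| BMI | 2.8% | 7.9% | exponent 0.25 | 1.028^0.25 = 1.007; 1.079^0.25 = 1.019 |
| Sex | none (exact match) | none | any | 1.00 |

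These shifts are small against 1.38.

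**3. Performance with matching as written** (8,000 data sets per row, SD 0.391, 8 per cohort):

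| Assumed effects | Coverage, class-only | Coverage, adjusted | RMSE, class-only | RMSE, adjusted |
|---|---|---|---|---|
| None | 0.900 | 0.899 | 0.1955 | 0.1987 |
| Age 0.5%/year, sex 1.2-fold, BMI exponent 0.25 | 0.913 | 0.899 | 0.1955 | 0.1980 |
| Age 1%/year, sex 1.3-fold, BMI exponent 0.25 | 0.926 | 0.903 | 0.1962 | 0.1972 |

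The planned model holds at least 90% coverage and its estimate is no less accurate. Where the covariates matter, it errs towards a slightly wide interval.

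**4. Looser matching.** Suppose the controls match Cohort A only and the moderate/normal ratio is examined, or the controls match a mix of A and B subjects. Class-only coverage was then 0.896–0.916, against 0.895–0.905 adjusted. Adjusted RMSE was worse or equal unless large effects were assumed; with no effect it was 0.214 against 0.195.

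**5. What it takes to cause harm.** A sex imbalance of k subjects in 8 multiplies the ratio by effect^(k/8). For assumed 1.2- and 1.3-fold effects (20,000 data sets each, age and BMI unmatched):

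| k | Factor on the ratio | Class-only coverage | RMSE, class-only | RMSE, adjusted |
|---|---|---|---|---|
| 2 | 1.047 / 1.068 | 0.900 / 0.899 | 0.200 / 0.208 | 0.211 / 0.212 |
| 3 | 1.071 / 1.103 | 0.890 / 0.881 | 0.207 / 0.219 | 0.217 / 0.217 |
| 4 | 1.095 / 1.140 | 0.878 / 0.849 | 0.214 / 0.236 | 0.227 / 0.230 |

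For age at 0.5 / 1% per year, with impaired subjects 0–10 years older than their controls throughout, coverage stays at 0.897 / 0.897. It reaches 0.894 / 0.873 only when all eight are 9–10 years older. With no covariate effect, adjustment widens the interval by 17% at k = 4 and by 19% at that age limit.

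**The case for a change.** The best argument for the concern is that one group of about eight controls cannot always be sex-matched to two cohorts at once. If the two impaired cohorts were independent draws with sex proportion 0.5 to 0.8 (assumed), their sex counts would be equal in only 20–25% of cases. At 0.5 the difference in counts is Binomial(16, 0.5) minus 8. It is 3 or more in 1 − (12,870 + 2 × 11,440 + 2 × 8,008)/65,536 = 21% of draws. It is 4 or more in 21% less 2 × 4,368/65,536 = 13.3%, so about 8%. Optional replacement of dropouts, and AUC(0-inf) values withheld under SAP 6.2.3, could loosen the balance further. The addendum also shows that analyses were added after database lock, so an adjustment made then would be open to the charge of being data-driven.

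Part of this stands. No adjusted model is named, and the allowance for extra analyses in SAP 6 is not prespecification. But those draws describe controls tied to one cohort only, whereas protocol 9.2 asks for matching to both, and the minimum of eight allows more controls to be added. The one-cohort case was checked in step 4 and coverage held. Even at fixed imbalances of 2 to 4 in 8, adjustment gives the larger RMSE in four of the six scenarios, and its best gain is 0.006.

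A sensitivity model beside an unchanged primary model would not settle the matter either. It would yield a second ratio with no rule for when the two differ, so judgement would still follow the data. An imbalance would not be hidden: it would show in the by-cohort baseline table, and SAP 6 requires any added analysis to be justified in the study report. The ratios are also not the only basis for dosing advice: "a population PK analysis applied to data from phase 2 and 3 studies will also be utilized to formulate a comprehensive dosing recommendation". That is a separate input and not a check on this trial.

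The wording of protocol 9.4.3 is no contradiction. A rule that each control must match an impaired subject is compatible with a control cohort matched to Cohorts A and B, and inclusion criterion 6 is worded in much the same way.

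**Conclusion.** The concern does not hold. It is true that the model contains hepatic class alone and that no adjusted analysis is prespecified, but no wrong number, rule or result follows. Controlling age, sex and BMI by matching and then estimating the ratios with a class-only model is a legitimate choice for a 24-subject study that protocol 7.2.1 describes as estimation-based. Followed as written, the plan gives 90% intervals with simulated coverage of 0.900 to 0.926, and 0.896 to 0.916 under looser matching. Point estimates are as accurate as adjusted ones, or more so, unless large covariate effects are assumed. Adjustment would use 3 of 21 error degrees of freedom and, with no covariate effect, would widen the interval by about 2% when matching works.

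This rests on matching being carried out broadly as protocol 9.2 describes and on moderate covariate effects (up to 1% per year of age, 1.3-fold for sex, BMI exponent 0.25). These effects are assumed. A sex imbalance of 3 or 4 in 8, or ages all at one edge of the caliper, would lower coverage to about 0.85 to 0.89 under the assumed effects. That would be a failure or an extreme of the matching, visible in the planned baseline tables. An adjusted model is a reasonable optional addition, and its absence is not a fault.
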